The overall objective of the research is to identify hormonal determinants of alcohol effects on brain activation during response inhibition (BARI) in young adult female and male drinkers. BARI will be assessed using fMRI during performance of the stop signal task. This task reliably activates right-lateralized prefrontal regions implicated in inhibitory control. We will assess BARI during IV alcohol (60mg%) and saline infusion in women during the early follicular and mid-luteal phases and in men at matched intervals. Aim 1: To determine the influence of circulating sex hormones on BARI responses to alcohol. Based on the positive relation between estradiol and BARI in sober heavy drinking women, we hypothesize that baseline levels of estradiol will be positively related to BARI following alcohol. Aim 2: To determine the effects of menstrual cycle phase on BARI responses to alcohol. We hypothesize that women will be more sensitive to the impairing effects of alcohol on BARI in the early follicular phase, when hormone levels are low. Aim 3: To determine the degree to which alcohol effects on sex hormones influence alcohol effects on BARI. We hypothesize that less alcohol-induced increase in estradiol will predict greater alcohol-induced decrease in BARI. Aim 4: To determine sex differences in BARI responses to alcohol. Based on our previous findings that heavy drinking women show less BARI than men when sober, we hypothesize that women will display greater alcohol-induced decrease in BARI than men, and that the sex difference will be most pronounced for women in the early follicular phase.

Study Design

Describe and explain the study design (e.g., observational, secondary analysis, single/double blind, parallel, crossover, deception, etc.).

- *Clinical Research:* Indicate whether subjects will be randomized and whether subjects will receive any placebo.
- *Community-Based Participatory Research:* If you are conducting [community-based participatory research \(CBPR\)](#), describe strategies for involvement of community members in the design and implementation of the study, and dissemination of results from the study.
- *Qualitative research:* Indicate ranges where flexibility is needed, if a fixed interview transcript is not available, describe interview topics including the most sensitive potential questions.

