- *Research Repositories:* If the purpose of this submission is to establish a Research Repository (bank, registry) and the material you plan to collect is already available from a commercial supplier, clinical lab, or established IRB approved research repository, provide scientific justification for establishing an additional repository collecting duplicate material. Describe the repository design and operating procedures. For relevant information to include, see the [UK Research Biospecimen Bank Guidance](#) or the [UK Research Registry Guidance](#).

This study will use a within- and between-subjects, placebo-controlled, single-blind design in a sample of female (N=30) and male (N=30) young adult heavy drinkers. Subjects will attend four fMRI sessions (two in the early follicular phase and two in the mid-luteal

phase for women, and at matched intervals for men) in which they perform the stop signal task and a resting state undergoing either IV alcohol (60mg%) or saline infusion (placebo). Alcohol and saline sessions within each phase will be separated by 24-48 hours. Dose and phase order will be counter-balanced. Blood samples will be collected at baseline and during infusion to assess levels of estradiol, progesterone, and testosterone. The primary outcome measure will be brain activation during response inhibition.

Attachments

Subject Recruitment Methods & Advertising

Describe how the study team will identify and recruit subjects. Please consider the following items and provide additional information as needed so that the IRB can follow each step of the recruitment process.

- How will the study team identify potential participants?
- Who will first contact the potential subjects, and how?
- Will you use advertisements? If so, how will you distribute those?
- How and where will the research team meet with potential participants?
- If applicable, describe proposed outreach programs for recruiting women, minorities, or disparate populations.
- How will minimize undue influence in recruitment?
- Attach copies of all recruiting and advertising materials (emails, verbal scripts, flyers, posts, messages, etc.).

For additional information on recruiting and advertising:

- [IRB Application Instructions - Advertisements](#)
- [PI Guide to Identification and Recruitment of Human Subjects for Research](#)

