**Attachments**

Attach Type	File Name
Study Drug Form	Ethanol_Side Effects, Dosages, Treatment, Interactions, Warnings.pdf
Study Drug Form	Study.Drug.Form.pdf
Study Drug Form	Alcohol_monograph.pdf
Study Drug Form	CofA Lot# 01RM1504A Ethanol.pdf
Study Drug Form	Ethanol_Label_Primary.pdf

Statistical Analysis Plan. *Statistical Analysis of Brain Activation:* The measures of brain activation during response inhibition (BARI) are activation in frontal ROIs (e.g., DLPFC, IFC, ACC, pre-SMA, SMA, and pre-motor cortex), as measured by BOLD % signal change, examined during response inhibition [StopInh>Go]. We will first check that men and women are matched on demographics and drug and alcohol use, and confirm that the [StopInh>Go] contrast activated the inhibitory network circuitry.

Statistical Analysis of Brain Activation: We will perform regression analyses in SPM12 to assess the degree to which baseline hormone levels predict change in BARI following alcohol compared to saline [StopInh>Go, Saline>Alcohol]. We hypothesize that greater baseline E2 will predict less activation following alcohol compared to saline. We will conduct a between-subjects t test to compare men and women on the StopInh>Go, Saline>Alcohol contrast. We hypothesize that alcohol effects on BARI will be greater in women compared to men. Finally, we will calculate change scores (alcohol minus baseline) for hormone levels, and perform regression analyses to predict [StopInh>Go, Saline>Alcohol] from change in hormone levels. We hypothesize that greater alcohol-induced increase in E2 will predict greater decrease in activation following alcohol.

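### The Aim 3 regression on raw hormone change has no baseline hormone term, so an effect of baseline level alone could appear as an alcohol-induced hormone effect

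*Combined protocol and SAP*

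**What the plan says.** The Statistical Analysis Plan (Statistical Analysis of Brain Activation) describes two separate regressions on one outcome, the Saline>Alcohol difference in StopInh>Go activation.

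- **Aim 1** uses the baseline hormone level as predictor: "We hypothesize that greater baseline E2 will predict less activation following alcohol compared to saline".
- **Aim 3** uses the raw difference: "we will calculate change scores (alcohol minus baseline) for hormone levels, and perform regression analyses to predict [StopInh>Go, Saline>Alcohol] from change in hormone levels". The expected direction follows: "We hypothesize that greater alcohol-induced increase in E2 will predict greater decrease in activation following alcohol".

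No covariate is named for the Aim 3 model. The Data Monitoring Plan adds only that general linear models and regression will be run in SPM and SPSS.

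The Objectives state Aim 3 as "To determine the degree to which alcohol effects on sex hormones influence alcohol effects on BARI", but give the opposite expectation: "less alcohol-induced increase in estradiol will predict greater alcohol-induced decrease in BARI".

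On data, the Study Design section says: "Blood samples will be collected at baseline and during infusion to assess levels of estradiol, progesterone, and testosterone". The baseline value is therefore available for every change score. The study is planned "in a sample of female (N=30) and male (N=30) young adult heavy drinkers". The SAP does not say whether the Aim 3 regression uses women only or both sexes, or how the two cycle phases enter it.

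**The concern.** Baseline is one half of the predictor, because the change score subtracts it. Absolute change will often depend on the starting level. If alcohol shifts E2 by a roughly constant percentage, women with higher baselines show larger absolute rises. If levels drift back toward a personal mean between samples, those with high baselines show smaller rises or falls.

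The SAP's own Aim 1 hypothesis is that baseline E2 is related to the same outcome. If that is true, and change is correlated with baseline, the slope on change picks up part of the baseline effect even when the alcohol-induced change has no influence on brain activation.

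Aim 3 is meant to say something different from Aim 1: that the hormonal response to alcohol, not the resting level, matters. Without a baseline term, a significant Aim 3 slope could be Aim 1 seen a second time.

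**Working it through.** **No figure to reproduce.** The documents give no alpha, effect size, power, hormone value or assay precision for this analysis. Everything numerical below is assumed, with ranges.

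**Step 1: the identity.** If the outcome Y depends on baseline B only, and C is change, then

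corr(Y, C) = corr(Y, B) × corr(B, C).

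This is zero only if one factor is zero. Example: 0.4 × 0.55 = 0.22. With n = 30, Fisher's z is atanh(0.22) × √27 = 0.2237 × 5.196 = 1.16. The chance of exceeding 1.96 is P(Z > 0.80), about 21%, against a nominal 5%.

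**Step 2: which sign for corr(B, C)?** With equal variances at the two times and correlation ρ between them, corr(B, C) = −√((1−ρ)/2). This is −0.22 at ρ = 0.9 and −0.50 at ρ = 0.5. A proportional alcohol effect pushes it positive. Both signs are plausible.

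**Step 3: rejection rates over a grid.** Two-sided 5%, no true effect of change, no assay error, 4,000 runs per setting. Columns give the absolute value of corr(B, C).

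| N | corr(Y, B) | 0 | 0.3 | 0.5 | 0.7 |
|---|---|---|---|---|---|
| 30 | 0.3 | 5% | 7% | 12% | 21% |
| 30 | 0.5 | 5% | 12–13% | 26% | 49% |
| 60 | 0.3 | 5% | 11% | 21% | 37% |
| 60 | 0.5 | 5–6% | 20–21% | 49% | 80–81% |

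With baseline in the model the rate is 4% to 6% in every cell.

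**Step 4: a hormone-like model.** Assumed: n = 30 women, one observation each; log-normal baseline; outcome correlated 0.4 with log baseline; percentage change independent of baseline with SD 10%; 20,000 runs per row.

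| Baseline log-SD | Mean rise | Assay CV | Raw change alone | Log ratio + log baseline | Log ratio alone |
|---|---|---|---|---|---|
| 0.35 | 10% | 0 | 10.5% | 4.8% | 4.8% |
| 0.35 | 20% | 0 | 21.4% | 4.9% | 5.2% |
| 0.6 | 10% | 0 | 16.4% | 4.9% | 4.7% |
| 0.6 | 20% | 0 | 31.5% | 4.9% | 4.9% |
| 0.35 | 10% | 8% | 7.4% | 5.7% | 4.9% |
| 0.35 | 20% | 8% | 12.6% | 5.7% | 5.0% |
| 0.6 | 10% | 8% | 10.8% | 5.3% | 5.0% |
| 0.6 | 20% | 8% | 20.3% | 5.1% | 4.8% |
| 0.35 | 10% | 15% | 6.6% | 8.6% | 5.2% |
| 0.35 | 20% | 15% | 8.2% | 8.4% | 5.0% |
| 0.6 | 10% | 15% | 8.5% | 6.2% | 4.9% |
| 0.6 | 20% | 15% | 13.1% | 6.5% | 5.0% |

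Repeat runs move the ends by one or two percentage points, so I quote 10% to 33% without assay error and 7% to 21% at 8% CV. With a mean change of zero, raw change alone rejects 5.5% to 6.8%.

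**Step 5: direction.** Code the outcome so that a positive value is a drop under alcohol. The SAP then expects a positive slope on baseline. If change rises with baseline, a baseline effect alone gives a positive slope on change, which is the SAP's Aim 3 prediction. If change falls with baseline, it gives a negative slope, which is the Objectives' Aim 3 prediction.

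**The case against.** Several stronger readings are tempting, and the documents do not support them.

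- **That the SAP states baseline E2 predicts the outcome.** It only hypothesizes this. If the hypothesis is false, there is nothing to leak into the Aim 3 slope.
- **That a baseline effect would necessarily produce the SAP's predicted result.** This needs change to rise with baseline. Under regression to the mean the bias runs the other way.
- **That scanning women in a low-hormone and a high-hormone phase makes it worse.** Pooling phases would widen the baseline spread, but the SAP does not say they are pooled. Analysis by phase would narrow it.
- **That Aims 1 and 3 cannot be told apart at all.** Both regressions are planned and baseline is assayed. If change is unrelated to baseline, there is no distortion.
- **That baseline adjustment is a complete cure.** At 15% assay CV the adjusted model rejects about 6% to 9%, and at log-SD 0.35 it is no better than raw change. In a separate check with assay reliability of 0.80, adjusted rates reached 15%. If all observed change is assay noise, the unadjusted test stays near nominal (4% to 7%) and adjustment can do worse.

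A further fair point is that, in the model of Step 4, the log ratio alone holds the 5% level. That follows from assuming percentage change is independent of baseline. It does not protect against regression to the mean or a non-proportional response, so it serves better as a sensitivity analysis than as the replacement.

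All of this limits the size and certainty of the problem. It does not supply a reason to leave baseline out.

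**Conclusion.** The point holds as a conditional one. The Aim 3 model as written names raw change as its only predictor, and nothing elsewhere in the documents adds the baseline level. A baseline effect alone could then be read as an alcohol-induced hormone effect, in either direction.

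The false-positive rates in Step 4 depend on two things the documents do not establish: a real baseline effect (taken as a correlation of 0.4) and a true change that is correlated with baseline. An observed correlation near zero is not enough to rule the problem out when the assay is noisy. In the row with log-SD 0.35, a 20% rise and 15% CV, the observed correlation was 0.00 and raw change still rejected 8.2%.

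The opposite Aim 3 hypotheses in the Objectives and the SAP add to the difficulty. Either sign of slope matches one of the two predictions, and the sign alone cannot separate a baseline effect from a change effect.

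**What to change.** In the SAP's Aim 3 sentence, add the baseline level of the same hormone as a covariate. Preferably express change as the log ratio of the on-infusion to the baseline value, and enter baseline on the log scale. State that Aim 3 is read from the slope for change adjusted for baseline. Report the log ratio without the baseline term as a sensitivity analysis, and report assay precision so that readers can judge the residual bias. State which participants and which cycle phases enter the model.

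Reconcile the Aim 3 hypothesis between the Objectives and the SAP before the data are analyzed.

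The cost is small: a sentence or two, no new samples, one degree of freedom and a slightly wider interval where change and baseline are correlated. The real drawback is some residual or induced bias when the baseline assay is noisy (about 6% to 9% rejection at 15% CV), which is why the sensitivity analysis is worth keeping.

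Baseline adjustment does not address a separate gap: the change score uses the alcohol session only and is not compared with change under saline.
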